#### Sample size

To gain short term and long term user feedback on the usability and for the evaluation of the primary and secondary objectives of this clinical study, it is expected that approximately 45 patients will need to undergo a procedure with the study device.

### 5.2. Secondary objectives

#### 5.2.1. Secondary objective: Radiation

#### Objective

Assessing radiation usage during PCI with the aid of Dynamic Coronary Roadmap

#### Endpoint

The endpoint is amount of radiation used during the PCI procedure. This will be defined as DAP fluoro (mGy cm^2), DAP exposure (mGy cm^2), DAP total (mGy cm^2), AK total (mGy).

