### 4.4. Procedures

Patients will receive standard medical treatment for their cardiac condition. During routine procedures, the physician may take angiograms for diagnosis which also serve as reference for device navigation. These angiograms will be automatically processed in the Dynamic Coronary Roadmap software and displayed as an overlay on the fluoroscopy for navigation support. In case a balloon catheter is used, the physician may take cine images when deflating the balloon as part of the standard care. These images can automatically be enhanced with the software and displayed. There is no follow up required after the procedure.

Phase 1: This is the phase where the physicians and study personnel can get used to the device and its capabilities. This phase serves to gain experience with the device and define workflow changes for the second phase. The use of Dynamic Coronary Roadmap makes these workflow changes possible and necessary in order to reduce the amount of contrast volume. It is estimated that 20 patients are necessary to gain enough experience and assess the workflow improvements.

Phase 2: This phase will focus on the contrast volume reduction. The defined workflow changes from phase 1 will be implemented in order to reduce the use of contrast volume. The minimal amount of contrast and timing of dosing will be defined. All other doses need to be avoided, as long as clinically acceptable. It is estimated that 25 patients are necessary to gain enough data to support the primary endpoint. This dataset will be compared with retrospective data from 25 patients that were treated without Dynamic Coronary Roadmap, preferably in the same timeframe.

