#### Experimental design

The objective is descriptive with no performance requirements and no pass or fail criteria. All Phase 2 subjects will be included in this analysis.

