#### Presentation format

Philips IGT Systems  Status: Final	Post-Market Clinical Study Plan  Contrast volume reduction during PCI with the use of Dynamic Coronary Roadmap	XCY607-130198 2017 Aug 15 Revision: 1.0 Page 12 of 16
---	---	--

Results will be described in summary statistics with median, confidence interval and standard deviation. Depending on the amount of data gathered during the clinical study a student t-test can be performed.

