### 5.2.2. Secondary objective: Demographics

#### Objective

Collecting patient demographics to further define the study population

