#### Endpoint

The endpoint is the demographical information of the study population. This will be defined as medical status and history, age, BMI and gender.

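### Section 5.2.1 measures radiation by dose alone and names no size adjustment, so a systematic body-size difference from the retrospective group would bias the DAP and AK comparison

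*Protocol*

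**What the plan says.** The radiation objective in Protocol section 5.2.1 is "Assessing radiation usage during PCI with the aid of Dynamic Coronary Roadmap". The endpoint paragraph reads "The endpoint is amount of radiation used during the PCI procedure" and gives a closed list that begins "This will be defined as DAP fluoro" and continues with DAP exposure, DAP total and AK total. All four are dose quantities. Neither fluoroscopy time nor a count of exposure runs is named anywhere in the protocol. The only timing endpoints, in 5.2.3, are catheter insertion to removal and time to first stent.

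The analysis is summary statistics with a confidence interval, plus an optional test: "Depending on the amount of data gathered during the clinical study a student t-test can be performed". On the analysis set, 5.2.1 says "All Phase 2 subjects will be included in this analysis".

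BMI appears only in 5.2.2, whose objective is "Collecting patient demographics to further define the study population" and whose endpoint reads "This will be defined as medical status and history, age, BMI and gender". Nothing links it to the radiation result.

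Section 4.1 describes a non-randomized study whose results are compared with data from before the roadmap was installed. Section 4.4 gives the size of that comparison: "This dataset will be compared with retrospective data from 25 patients that were treated without Dynamic Coronary Roadmap, preferably in the same timeframe". No matching rule is stated.

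**The concern.** The roadmap is an overlay on live fluoroscopy, and Phase 2 deliberately changes the workflow to lower contrast. A natural radiation question is whether the operator then uses more or less X-ray. Dose answers this only after passing through the patient's body: for the same beam-on time and the same runs, a larger patient generally receives more dose. That is general X-ray physics and is not stated in the protocol.

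If Phase 2 subjects differ systematically in size from the retrospective patients, a DAP or AK difference mixes that with any effect of the roadmap, and no listed measure of X-ray use is free of patient size. The Summary says the secondary information will be used in designing the pivotal trial, so a confounded difference could be carried forward.

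**Working it through.** **The plan's own figures.** The protocol gives no alpha, power, effect size or SD, so there is no power calculation to reproduce. The counts agree: 20 in Phase 1 plus 25 in Phase 2 is 45. The comparison is 25 v 25.

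**Assumed inputs (none is in the protocol).** BMI SD 4 to 6 kg/m2; SD of log DAP 0.6; DAP rising by 3% to 8% per BMI unit.

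**Step 1: chance imbalance.** The standard error of the difference in mean BMI is SD × sqrt(2/25). For SD 4, 5 and 6 it is 1.13, 1.41 and 1.70, so the 95% chance range is ±2.22, ±2.77 and ±3.33. A gap of 2 units or more arises by chance with probability 8%, 16% and 24%.

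This variation is already part of the spread of DAP. With log-DAP SD 0.6, the 95% half-width of the unadjusted difference is 1.96 × 0.6 × sqrt(2/25) = 0.33 on the log scale, a ratio of about 0.72 to 1.39. Chance differences in BMI are inside that interval and do not raise the error rate of the t-test (first three rows of the table).

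**Step 2: systematic imbalance.** If the roadmap group is leaner by d units on average and dose rises by a fraction g per unit, the unadjusted comparison shows a false reduction of 1 − (1+g)^(−d).

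- d = 2: 5.7%, 9.3% and 14.3% for g = 3%, 5% and 8%.
- d = 3: 8.5%, 13.6% and 20.6%.

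A simulation with no device effect (25 v 25, BMI SD 5, log-DAP SD 0.6, 20,000 replicates per row) agrees:

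| Mean BMI gap (roadmap group leaner) | Dose per BMI unit | Unadjusted DAP change | Unadjusted t-test, false positives | BMI-adjusted, false positives |
|---|---|---|---|---|
| 0 | 3% | about 0 | 5.0% | 5.1% |
| 0 | 5% | about 0 | 4.9% | 5.0% |
| 0 | 8% | about 0 | 5.2% | 5.0% |
| 2 | 3% | −5.5% | 6.1% | 5.0% |
| 2 | 5% | −9.2% | 8.4% | 5.0% |
| 2 | 8% | −14.4% | 14.6% | 4.8% |
| 3 | 3% | −8.7% | 8.1% | 4.8% |
| 3 | 5% | −13.5% | 13.1% | 5.0% |
| 3 | 8% | −20.6% | 26.2% | 4.8% |

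With BMI in the model the average bias is within 0.3% of zero in every row. The gaps of 2 and 3 units are imposed for illustration; the protocol gives no evidence that such a gap exists, or in which direction.

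**Step 3: precision gained by adjusting.** The interval narrows by 1 − sqrt(1 − (slope × SD)²/0.6²), with slope on the log scale. This is 2% at SD 4 and slope 0.03, 7% at SD 5 and slope 0.045, and 20% at SD 6 and slope 0.06. The main reason to adjust is bias; the gain in precision is modest.

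**The case against.** The case on the other side is substantial, and much of it stands.

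- *Objective against endpoint.* A reader might infer that an objective of radiation usage is contradicted by dose-only endpoints. The protocol does not support this. Its Summary names radiation dosage as the secondary endpoint, and 5.2.1 itself treats usage as amount of radiation. The list is incomplete for a non-randomized comparison, but it is not inconsistent.
- *Chance alone.* A reader might take the chance BMI range in Step 1, convert it to a DAP difference of roughly 7% (exp(0.03 × 2.22) = 1.069) to 22% (exp(0.06 × 3.33) = 1.221), and call that a spurious roadmap effect. It is ordinary sampling noise, already covered by the interval that 5.2.1 promises.
- *The fluoro/exposure split.* Size raises both components, so a shift from exposure runs to fluoroscopy would show partly in their relative share. This stands, but the share says nothing about whether total X-ray use rose or fell.
- *BMI is not ignored.* It is summarised under 5.2.2, where a t-test is also allowed, so an imbalance might be noticed. But 5.2.2 covers Phase 2 subjects, nothing says that BMI is taken for the retrospective patients, and noticing an imbalance does not correct the estimate.
- *Matter for a SAP.* Covariate adjustment could sit in a SAP that is not shown, so this is the weaker half of the point. The endpoint list is fixed in the protocol, and a later SAP cannot supply measures that were never collected.
- *No clean attribution.* Fluoroscopy time and run count also depend on lesion complexity and operator. This stands: they are useful beside dose, not a cure for confounding.
- *Inferred comparison.* Section 5.2.1 names only Phase 2 subjects. That radiation is compared with the retrospective group follows from sections 4.1 and 4.4 and from the optional t-test.

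**Conclusion.** The point holds in a limited form. Section 5.2.1 fixes a dose-only list and names only an unadjusted test, in a non-randomized comparison with 25 retrospective patients and no stated matching. A systematic difference in body size would bias the DAP and AK contrast: by about 6% to 14% for a 2-unit BMI gap and about 9% to 21% for a 3-unit gap, if dose rises 3% to 8% per unit. Both the slope and the gap are assumptions. The protocol does not show that the groups will differ in size, only that nothing in it would prevent or correct such a difference. Severity is low: the endpoint is secondary and descriptive with no pass/fail rule, and the point matters mainly because the results are to inform the pivotal trial.

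**What to change.** In section 5.2.1:

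1. Add fluoroscopy time and number of exposure runs, for Phase 2 and retrospective patients, as size-independent measures of X-ray use shown beside dose.
2. State that BMI will also be recorded for the 25 retrospective patients.
3. Replace the raw t-test with a regression of log DAP and log AK on group and BMI, reporting the adjusted difference with its interval and the unadjusted figure beside it.

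The cost is a short addition to the text, a few data fields (assumed to be logged by the X-ray system), BMI abstraction for 25 patients and one model degree of freedom. Differences in lesion complexity and operator would remain unadjusted, and the report should say so.

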#### Experimental design

The objective is descriptive with no performance requirements and no pass or fail criteria. All Phase 2 subjects will be included in this analysis.

#### Presentation format

Philips IGT Systems  Status: Final	Post-Market Clinical Study Plan  Contrast volume reduction during PCI with the use of Dynamic Coronary Roadmap	XCY607-130198 2017 Aug 15 Revision: 1.0 Page 12 of 16
---	---	--

Results will be described in summary statistics with median, confidence interval and standard deviation. Depending on the amount of data gathered during the clinical study a student t-test can be performed.

### 5.2.2. Secondary objective: Demographics

#### Objective

Collecting patient demographics to further define the study population

#### Endpoint

The endpoint is the demographical information of the study population. This will be defined as medical status and history, age, BMI and gender.

#### Experimental design

The objective is descriptive with no performance requirements and no pass or fail criteria. All Phase 2 subjects will be included in this analysis.

#### Presentation format

Results will be described in summary statistics with median and standard deviation. Depending on the amount of data gathered during the clinical study a student t-test can be performed.

### 5.2.3. Secondary objective: Procedure efficiency

#### Objective

Assessing procedure efficiency

#### Endpoint

The endpoint is procedural timing. This is defined as the time from start of the procedure (catheter inserted) until end of the procedure (catheter removed) and time until first stent is placed.

#### Experimental design

The objective is descriptive with no performance requirements and no pass or fail criteria. All Phase 2 subjects will be included in this analysis.

#### Presentation format

Results will be described in summary statistics with median, confidence interval and standard deviation. Depending on the amount of data gathered during the clinical study a student t-test can be performed.

### 5.2.4. Secondary objective: Procedural information

#### Objective

Collecting procedural information to further define the study population

#### Endpoint

The endpoint is procedural information. This is defined as information on treated vessels, number of lesions, number of stents, type of lesion, catheter access site, lesion complexity, IVUS usage, OCT usage and FFR usage. These endpoints are typically recorded for patients undergoing coronary interventions, also for non-study patients.

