## 4. STUDY DESIGN

### 4.1. General

This is a prospective, non-randomized, unblinded, observational, single-center study.

A non-randomized study design has been chosen to get first insights in contrast reduction with the use of Dynamic Coronary Roadmap. This study will serve as a pilot study to power a pivotal study at a later stage.

The results of the study population will be compared with retrospective data generated before the Dynamic Coronary Roadmap was installed.

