## 6. DATA MANAGEMENT

Electronic Case Report Form (e-CRF) will be used to collect medical history, subjects demographics, procedure related information, protocol deviations, adverse events and device deficiencies. The e-CRF will be used for data review, data cleaning and issuing and resolving queries. This e-CRF is a web-based e-CRF which is password protected and is 21 CFR part 11 compliant. At the end of the study the data will be stored as a frozen dataset and will be retained.

Raw image data is collected directly from the detector, and therefore is free from any subject information. All other exported data will be de-identified. This data will be collected and stored in a secure location.

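### The retrospective controls are not tied to the Phase 2 operators and the operator is not a listed item, so a difference in operator mix could pass as contrast reduction

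*Protocol*

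**What the plan says.** Section 4.1 describes the design: "This is a prospective, non-randomized, unblinded, observational, single-center study". It also places the comparison data before installation: "The results of the study population will be compared with retrospective data generated before the Dynamic Coronary Roadmap was installed".

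Section 4.4 gives the rule for choosing controls: "This dataset will be compared with retrospective data from 25 patients that were treated without Dynamic Coronary Roadmap, preferably in the same timeframe". The only selection preference is about time. Neither section says which physicians must have treated the control patients.

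Section 4.4 also shows that the operator matters. Of Phase 1 it says "This is the phase where the physicians and study personnel can get used to the device and its capabilities", and workflow changes are worked out there over about 20 cases. In Phase 2 those changes are applied and a minimal contrast scheme is set; beyond it, "All other doses need to be avoided, as long as clinically acceptable".

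The recorded items are set out in three places. Section 5.2.4 lists "treated vessels, number of lesions, number of stents, type of lesion, catheter access site, lesion complexity, IVUS usage, OCT usage and FFR usage". Section 5.2.2 says of the demographics "This will be defined as medical status and history, age, BMI and gender". Section 6 describes the e-CRF more loosely, as covering medical history, demographics and "procedure related information, protocol deviations, adverse events and device deficiencies". None of the three names the operator.

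Section 5.1 calls the objective descriptive, without pass or fail criteria. It plans summary statistics and leaves a Student t-test optional.

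**The concern.** How much contrast is given is decided by the person doing the case, and Phase 2 works by asking that person to give less. Some physicians may already use less or more than their colleagues. If the Phase 2 cases and the retrospective cases were done by different physicians, or by the same physicians in clearly different shares, that habitual difference is added to the device estimate. It can go in either direction.

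Adjusting for lesions, stents or access site does not remove it. A reader holding only the listed variables could not tell whether it was there.

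The absence of a pass or fail criterion does not remove the problem. The Summary and 4.1 say the study is meant to power a later pivotal study, and 3.1 links it to a possible contrast reduction claim. The estimated difference and its spread are what this study passes on, and a confounded difference would carry over into the pivotal sample size.

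**Working it through.** **The plan's own figure.** 20 Phase 1 + 25 Phase 2 = 45 subjects, as stated in 4.3.4. The protocol gives no alpha, power, SD or effect size, so there is no power-based figure to reproduce.

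**Inputs.** From 4.4: 25 Phase 2 cases against 25 retrospective cases. Assumed, because the protocol gives none of them: the number of operators, their case shares, the between-operator share of variance (ICC, 0.02 to 0.20), and the size of any gap between operators. Results are in units of the total SD of contrast volume.

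**Reference precision.** The half-width of a 95% t interval is t(0.975; 48 df) × √(2/25) = 2.011 × 0.2828 = 0.57 SD.

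**Bias from operator mix.** False difference = operator gap × shift in case shares. The chance that a nominal 5% test is significant with no device effect is about Φ(b/0.2828 − 1.96) + Φ(−b/0.2828 − 1.96), where b is the false difference.

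| Gap (SD) | Share shift | False difference (SD) | Chance of significance |
|---|---|---|---|
| 0.3 | 0.4 | 0.12 | 7% |
| 0.5 | 0.4 | 0.20 | 11% |
| 1.0 | 0.4 | 0.40 | 29% |
| 1.0 | 0.6 | 0.60 | 56% |

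**Interval width.** Let w1 and w2 be an operator's shares of the cases in the two groups. Then

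- true variance of the difference = ICC × Σ(w1 − w2)² + (1 − ICC) × 2/25;
- expected t-test variance = (2/25) × [(1 − ICC) + ICC × m], where m is the average over the two groups of (25/24)(1 − Σw²).

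Worked case: two study operators (13 and 12 cases), controls from five operators including those two (5 cases each), ICC 0.10.

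- Σ(w1 − w2)² = 0.32² + 0.28² + 3 × 0.20² = 0.3008.
- True variance = 0.0301 + 0.0720 = 0.1021.
- m = (0.520 + 0.833)/2 = 0.677, so the t-test variance = 0.08 × 0.968 = 0.0774.
- Variance ratio 1.32; SE ratio 1.15.

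Coverage of the nominal 95% interval, from 40,000 simulated data sets per cell:

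| Who treats the two groups | Σ(w1 − w2)² | SE ratio, ICC 0.02 to 0.20 | Coverage % at ICC 0.02 / 0.05 / 0.10 / 0.20 |
|---|---|---|---|
| One operator, both groups | 0 | 1.00 | about 95 throughout |
| Same five, equal shares | 0 | 0.99 to 0.91 | 95.2 / 95.6 / 96.0 / 96.7 |
| Same five, mild shift (7,6,5,4,3 v reverse) | 0.064 | 1.00 | about 95 throughout |
| Same five, strong shift (10,8,4,2,1 v reverse) | 0.374 | 1.04 to 1.35 | 94.2 / 92.8 / 90.2 / 85.6 |
| Two v five including those two | 0.301 | 1.03 to 1.29 | 94.4 / 93.2 / 91.5 / 87.5 |
| Five v five different | 0.400 | 1.04 to 1.36 | 94.0 / 92.6 / 90.3 / 85.5 |
| Two v five different | 0.701 | 1.08 to 1.65 | 93.1 / 90.3 / 85.3 / 77.1 |

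The direction therefore depends on how operators are spread over the groups. The interval is too short when operators differ or their shares shift strongly. It is about right with one operator or a mild shift, and slightly too wide with the same operators in equal shares.

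**The case against.** Several points on the other side are sound.

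- **Number of operators.** The protocol does not give it. That more than one takes part rests on a plural in the Phase 1 text; elsewhere 4.2 and 4.4 speak of the physician in the singular. The contents page lists an Appendix I of investigators and sites, which was not in the text examined and cannot be held against the plan. If one operator does both sets of cases, the problem disappears. A reader might infer that Phase 2 is done by a few trained operators; 1.3 requires training but does not limit how many receive it.
- **Recording.** A reader might infer that the operator will not be recorded at all. Section 5.2.4 defines an endpoint, not the full data capture, and the e-CRF content in section 6 is not itemised. The operator may be held there or in source records. What stands is that the plan does not require it for either group.
- **Interval.** A reader might infer that the t-test interval is simply too narrow. The table shows that this is conditional. The t-test is itself optional, the confidence interval in 5.1 belongs to the summary statistics, and no between-group interval is specified. In a single-center study some overlap of operators is plausible, so the rows with entirely different operators are the unfavourable end.
- **Analysis model.** An operator term could be left to a statistical analysis plan, which is not at hand. Such a plan cannot supply a variable that was never collected, however, and it does not normally decide which control patients are drawn.

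These points limit the size of the problem and how certain it is. They do not answer the gap in the control rule.

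**Conclusion.** The point holds in conditional form. The control rule in 4.4 allows retrospective cases from any operator at the center, and neither 5.2.2 nor 5.2.4 lists the operator, although the primary endpoint is under the operator's control. If the operator mix differs, the contrast difference is confounded, and this cannot be checked from the listed variables.

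The possible bias runs from negligible to larger than the interval half-width of 0.57 SD; the top of that range needs a 1.0 SD gap with a 60-point shift. Coverage of a between-group interval, if one is computed, ranges from slightly above 95% down to 77% over the allocations shown. All of this rests on assumed ICCs, operator numbers, shares and gaps, so the actual size in this study is unknown.

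For a descriptive single-center pilot this is a cheap improvement, not a fatal flaw.

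**What to change.** - In 4.4, state that the retrospective cases are drawn from the operators who perform Phase 2, in similar proportions where possible.
- In 5.2.4, add the first operator as an item for both the Phase 2 and the retrospective cases.
- In section 5, report contrast by operator, and stratify or adjust by operator in any between-group comparison that is made, including radiation and procedure time.

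With five operators treating five patients each per group, the mix bias is zero and the plain t interval covers 95.2% to 96.7% for ICC 0.02 to 0.20; an operator term would recover the small loss of precision.

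The cost is one field, assumed to be available from the routine procedure record, and a few sentences. The downside is a smaller pool of eligible controls and a few degrees of freedom.
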